The aim of this study is to explore the role of the CDED combined with PEN in both inducing and maintaining remission of CD in adults, taking into consideration important objective biomarkers such as faecal calprotectin (FC) (21) along with patient reported outcomes. More precisely, our primary goal is to investigate whether CDED with PEN could lead to a significant decrease in feacal calprotectin concentration. In view of the existing dietary guidelines for adult Crohn's disease patients (7,8) and considering that dairy constitute the main dietary source of calcium, researchers wish to challenge patients in remission with a gradually increasing exposure to dairy products, to assess tolerability, prospecting for the development of a personalized remission maintenance diet based on the CDED principles. Our aim is to examine the proportion of patients with significant feacal inflammation elevation following the dairy introduction.

We intent to investigate the effectiveness and feasibility of this dietary strategy in terms of changes in clinical and biochemical indices, patient's quality of life and nutritional status as well as patients' adherence and acceptance of the diet. Finally, we plan to re-evaluate patients' dietary habits and clinical outcomes, 6 months after the beginning of the study to address the established dietary adaptations, as well as the sustainability and durability of potential benefits of the dietary intervention.

Design and Methods

The proposed project is a randomized controlled clinical trial which is held in Evangelismos General Hospital of Athensin collaboration with the Department of Food Science & Human Nutrition of Agricultural University of Athens. Briefly, eligible patients are adults with established Crohn's disease with ileal and/or colonic involvement who receive their IBD care at the hospital's Gastroenterology Unit (see eligibility criteria below). Patients with active mild-to-moderate disease, defined by aHarvey–Bradshaw Index (HBI) score of 5–14 points, or inactive disease (HBI<5) are eligible for enrolment. Detailed information about the purpose and the study procedures will be given to all patients and consent form will be signed. The study protocol has been approved by the Ethics committee of the hospital.

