Patients will be randomly assigned 1:1 to either CDED plus PEN plus dairy products or PEN plus usual nutritional care. In detail, half of the patients in remission will follow the first stage diet (CDED+PEN) for 4 weeks and will continue with CDED + PEN + dairy products for another 4 weeks. The other half will be given PEN plus the usual advice for a healthy dietary pattern. PEN will cover the 50% of total energy requirements for the first 4 weeks and the 25% during the second 4 weeks. Half of the patients with active disease will follow the first stage diet (CDED + PEN 50%) for 6 weeks and then, the responders will continue with adding the dairy product while PEN will cover 25% of the total energy requirements, for 4 more weeks. The other half will be given PEN plus the usual advice for a low residue diet. Low lactose, low fat and low additive dairy foods will be given, namely Greek yogurt 2% fat and light yellow cheese with 10-12% fat, in calculated portions to meet tailored energy, protein and calcium requirements. After the end of the intervention period, patients will be advised to reintroduce foods that were eliminated and to follow a maintenance diet. All participants will attend study visits at the beginning, in the middle (week 8 or week 10, for patients entering the study in remission or with active symptoms, respectively) and at the end of the study, at which points questionnaires will be completed, anthropometric measurements will be conducted and biological samples will be collected. The last follow-up will take place in week 24. In the meanwhile, phone calls by a researcher dietitian will be held to assess adherence and support the patients.24-hour diet recallsand the modified Medication Adherence Report Scale (MARS) questionnaire (16) will be used to address compliance along with the physician's assessment.

At length, our methodological approach includes:

i) Anthropometry

- (1) Weight (kg) measurement, [Time Frame: Baseline, week 4, week 8 (Baseline, week 6, week 10 for patients entering the study with active disease), week 24]
- (2) Height (m) measurement, [Time Frame: Baseline],
- (3) Body mass index (BMI) (kg/m²) calculation
- (4) Waist, neck and midarm circumferences (cm), triceps skinfold (mm) measurement [Time Frame: Baseline, week 8/w10]
- (5) Body composition analysis (Fat mass, fat %, fat free mass, phase angle)
 by Bioelectrical Impedance Analysis (BIA) [Time Frame: Baseline, week
 8/10]

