- (6) Handgrip strength (kg) assessment by dynamometer [Time Frame: Baseline, week 8/w10]
- Dietary habits assessment, using a semi-quantitative food frequency questionnaire (FFQ), to assess dietary habits and adherence to the Mediterranean diet (MD-score) [Time Frame: Baseline, week 24] and 24-

recalls [Time Frame: Baseline, week 2/w3, week 4/w6, week 6/w8, week 8/w10]

- iii) Physical activity assessment, using HPAQ questionnaire [Time Frame: Baseline, week 8/w10]
- iv) Health-related quality of lifeassessment, defined by the selfadministered 32-item Inflammatory Bowel Disease questionnaire (IBDQ) score. Higher IBDQ scores indicate better outcomes. Clinical response defined as increase ≥16 points [Time Frame: Baseline, week 8/w10]
- v) Medical history (e.g.,prior GI surgery, comorbidities) data collection and disease activity assessment by the HBI. Clinical response is defined as baseline HBI score decrease of ≥ 3[Time Frame: Baseline, week 4/w6, week 8/w10]
- vi) **Blood and Feacal samples collection** by specializes staff [Time Frame: Baseline, week 4/w6, week 8/w10]
 - (1) **Blood samples analysis** by the hospital's lab to estimate serum **CRP** and **albumin**
 - (2) Feacal samples analysis by certified labs to estimate Feacal calprotectin concentration (μ g/g)
- vii) Nutrition education according to the intervention principals and prescription of nutritional supplements (liquid formulas-PEN) [Time Frame: Baseline]. Support line for patients' support will be available.
- viii)**Handle-analysis** of the questionnaires and **data entry** in electronic databases [Microsoft® Excel, IBM SPSS Statistics®, Nutritionist Pro®]
- ix) Statistical analysis/interpretation of results.

Eligibility Criteria:

Inclusion Criteria:

- Participants must have an established diagnosis of CD
- Individuals able to give informed consent and willingness to participate Exclusion Criteria:
 - Age < 18 years old
 - Previous extensive bowel resection
 - Reported pregnancy or lactation
 - Current stoma or abscess
 - Clinically significant stricture
 - Introduction of or change in dose of drug therapy within the past 8 weeks

- Comorbidities including diabetes or coeliac disease, or other concomitant serious comorbidity e.g. significant psychiatric, hepatic, renal, endocrine, respiratory, neurological, cardiovascular, neoplastic or other autoimmune disease
- Food allergies or intolerances, which do not permit participation in the study

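### The dairy aim concerns patients in remission, but week-6 responders can start dairy with HBI 5 to 11, and the SAP does not measure FC elevation from the pre-dairy sample

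*Combined protocol and SAP*

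**What the plan says.** - **Aim (Objectives).** The researchers wish to "challenge patients in remission with a gradually increasing exposure to dairy products", looking towards a maintenance diet. The quantity of interest is the "proportion of patients with significant feacal inflammation elevation following the dairy introduction". No threshold for a significant elevation is given.
- **Cut-offs (Design and Methods).** Active mild-to-moderate disease is HBI 5 to 14; patients with "inactive disease (HBI<5) are eligible for enrolment".
- **Entry to dairy, active stratum.** After six weeks of CDED plus PEN at 50%, "the responders will continue with adding the dairy product while PEN will cover 25% of the total energy requirements, for 4 more weeks". The sentence gives no criterion and no cross-reference.
- **Entry to dairy, remission stratum.** After four weeks these patients "will continue with CDED + PEN + dairy products for another 4 weeks". No HBI condition is attached.
- **Response definitions.** Item iv, on the IBDQ: "Clinical response defined as increase ≥16 points [Time Frame: Baseline, week 8/w10". Item v, on the HBI: "Clinical response is defined as baseline HBI score decrease of ≥ 3", with HBI recorded at baseline, week 4 or 6, and week 8 or 10.
- **Samples (item vi).** Blood and stool are collected "by specializes staff [Time Frame: Baseline, week 4/w6, week 8/w10", so an FC value exists just before dairy starts.
- **SAP.** FC change is a percentage of each patient's baseline value. The logistic models include disease activity, but their outcome is a drop in HBI or FC. Chi-squared or Fisher tests are named for categorical variables in general. Neither FC elevation after dairy nor HBI at the start of dairy is mentioned.

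**The concern.** Two things do not line up with the dairy aim.

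The first is the population. The aim speaks of remission; the entry rule for active patients speaks of response. An HBI fall of 3 does not guarantee an HBI below 5. A single proportion over everyone who receives dairy can therefore mix patients in remission with patients whose disease is still active by the protocol's own cut-off. In the other direction, a patient who reaches remission by a small fall would not be given dairy, although the aim is about such patients.

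The second is the reference point. FC may fall during the CDED stage and rise again once dairy is added. A change measured from baseline combines the two stages, and the fall can hide the rise.

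Early dairy introduction is in the official title, and the result is meant to inform advice on maintaining remission. What is at stake is whether the reported figure answers that question.

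**Working it through.** **1. The plan's own figures.** The plan gives no figure for the dairy proportion. The only sample size is 140, which cannot be reproduced because the SAP states no effect size, SD, rates, test or dropout. It is used here only for a ceiling: 140 randomised 1:1 gives at most 140/2 = 70 dairy recipients, and fewer if some active patients do not respond.

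**2. Which response definition can apply at week 6.** The IBDQ is scheduled at baseline and week 8/10 only, so item iv cannot decide entry at week 6. FC and CRP are sampled then but have no response threshold. Item v is the only definition that can be applied.

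**3. What item v allows.** Let e be entry HBI (5 to 14) and w week-6 HBI (0 to e). Response is w ≤ e − 3; remission is w ≤ 4.

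| Entry HBI | Highest HBI of a responder | Responder but HBI ≥ 5 | Remission but not responder |
|---|---|---|---|
| 5 | 2 | none | 3, 4 |
| 6 | 3 | none | 4 |
| 7 | 4 | none | none |
| 8 | 5 | 5 | none |
| 9 | 6 | 5–6 | none |
| 10 | 7 | 5–7 | none |
| 11 | 8 | 5–8 | none |
| 12 | 9 | 5–9 | none |
| 13 | 10 | 5–10 | none |
| 14 | 11 | 5–11 | none |

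Possible pairs (e, w):
- Response: 3 + 4 + … + 12 = 75.
- Response with HBI ≥ 5: 1 + 2 + … + 7 = 28.
- Response and remission: 75 − 28 = 47.
- Remission: 10 × 5 = 50.
- Remission without response: 50 − 47 = 3.
- Either: 75 + 3 = 78, that is, 50 in remission and 28 not.

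These are possible scores, not patients. The documents give no HBI distribution.

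**4. Effect of mixing.** Let f be the share of dairy recipients with pre-dairy HBI ≥ 5. Then

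pooled proportion − proportion in HBI < 5 = f × (p≥5 − p<5).

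Both inputs are assumptions. With f = 5% and a difference of 10 points: 0.05 × 10 = 0.5 points. With f = 25% and 20 points: 0.25 × 20 = 5 points. The sign can go either way.

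**5. Effect of the reference sample.** If FC falls by a fraction a before dairy and then rises by a fraction b, the change from baseline is (1 − a)(1 + b) − 1. This is still negative whenever b < a/(1 − a). As an assumed illustration, if FC halves before dairy (a = 0.5), it can rise by anything short of 100% afterwards and still show as a drop from baseline.

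**6. Precision cost of reporting HBI < 5 alone.** The 95% CI widens by 1/√(1 − f): 1.026 at f = 5%, 1.054 at 10%, 1.155 at 25%. At the ceiling of 70 recipients and an assumed 20% with elevation, the half-width is 1.96 × √(0.2 × 0.8/70) = 9.4 points. With 70 × 0.95 = 66.5 it is 9.6, and with 70 × 0.75 = 52.5 it is 10.8.

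**The case against.** **The entry rule is defined.** Item v defines clinical response and is scheduled at the very visit where dairy entry is decided. This stands. A reader might infer that the rule is undefined, or that responders secretly means HBI below 5. The first is too strong, since what is missing is a cross-reference; the second is not written anywhere. But taking item v as the rule is exactly what lets in HBI 5 to 11.

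**The aim need not be limited to remission.** The sentence naming the proportion has no HBI limit; the remission limit comes from the sentence before it. Joining them is a reading, though a natural one, because the stated purpose is a maintenance diet for remission.

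**The SAP covers it.** A proportion with elevation is categorical, and the SAP names tests for categorical variables. This rules out saying that no method applies at all. The general sentence still fixes neither the reference sample nor the population.

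**The effect is small.** Even the largest assumed distortion, 5 points, is about half the 9.4-point half-width. This stands as a limit on importance. It does not touch the reference-sample problem.

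**The data will exist anyway.** HBI and FC are collected at the right visits, so the estimate could be produced later. But the reference sample and population would then be chosen with FC results in view.

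**Conclusion.** The point holds, confined to the dairy aim. Following the SAP as written would not measure the FC rise after dairy in patients in remission: the only stated FC change is from baseline, and nothing identifies who was in remission when dairy began. The HBI 5 to 11 range and the three omitted transitions (5 to 3, 5 to 4, 6 to 4) are exact, given that item v is the entry rule.

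The number of patients affected and the size of any distortion are unknown. The 0.5 to 5 points in the working rests wholly on assumed inputs. A reader might infer a bias of known direction, a threat to the primary FC goal, or a need to bar patients with HBI 5 or more from dairy. The documents support none of these: the sign is not fixed, the primary goal does not depend on this proportion, and a separate report is enough.

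**What to change.** 1. **Design and Methods, entry to dairy.** State that responders are patients with an HBI fall of 3 or more (item v) or an HBI below 5 at week 6. No week-6 remitter is then denied dairy.
2. **SAP.** Calculate FC elevation from the pre-dairy sample (week 4, or week 6 for active entrants) to week 8/10. Report the proportion among dairy recipients with pre-dairy HBI below 5, pooled over both strata, as the answer to the remission-maintenance aim. Describe recipients with HBI 5 or more separately. Because HBI is also checked at week 4, this covers remission entrants who are no longer below 5.

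The aim needs no rewording, and a four-cell report by stratum and HBI is not needed. Splitting the HBI < 5 group by stratum would cost precision: with an assumed 35 per stratum and 20% elevation, the half-width is 1.96 × √(0.16/35) = 13.3 points.

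No new visit or sample is required. The cost is the 3 to 15% wider interval under the assumed 5 to 25% share, and a group with HBI 5 or more that is likely to be small and can only be described. The change does not separate dairy from the simultaneous PEN step-down to 25%. A threshold for significant elevation must also be set before any such proportion can be calculated; that is a separate gap.

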- Any proven current infection such as positive stool cultures or positive tests for parasites or C. difficile.

The proposed project has a duration of thirty-six (36) months. The 1st phase that has already been completed included preparation and printing of questionnaires, creation of recipes based on the principles of the dietary intervention. The recruitment process is anticipated to start in September 2022 and to be completed by March 2024.

Statistical Analysis Plan (SAP)

Based on pilot data (18) we performed a sample size calculation using the GPower 3.0.10 software (http://www.softpedia.com/get/Science-CAD/G-Power.shtml). A sample of 140 individuals is sufficient to achieve statistical power > 80 %, at a significance level of a = 0,05 for two-sided statistical tests. All continuous variables will be assessed for normality with the Kolmogorov–Smirnov test (cutoff p < 0.01), to use parametric or non-parametric tests, as appropriate. Chi-squared or Fischer's test will be used to analyze categorical variables. Continuous variables will be analyzed by using Mann Whitney U test and t-test for paired-samples or the Wilcoxon signed rank). For paired measures (e.g. FC concentration) before and after the intervention, we will calculate the percentage change for each patient relative to baseline. Logistic regression models will be used to explore how age, sex, phenotypic factors (disease location and activity), MD-scoreat baseline, adherence and intervention grouping would contribute to significant HBI or FC concentration drop.

Bibliography:

3;396(10256):e56]. *Lancet*. 2017;390(10114):2769-2778. doi:10.1016/S0140-6736(17)32448-0

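### The HBI response rule names no population, so as written entrants scoring 0–2 cannot meet it, and no named HBI outcome measures remission induced or maintained

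*Combined protocol and SAP*

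**What the plan says.** Objectives gives the aim as exploring the exclusion diet with partial enteral nutrition "in both inducing and maintaining remission of CD in adults". Design and Methods admits two strata: active disease with HBI 5–14, "or inactive disease (HBI<5) are eligible for enrolment".

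Item v of the same section gives the only HBI response rule: "Clinical response is defined as baseline HBI score decrease of ≥ 3". Its time frame lists the visits of both strata: "decrease of ≥ 3[Time Frame: Baseline, week 4/w6, week 8/w10". No population is attached.

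The SAP plans logistic models of how age, sex, "phenotypic factors (disease location and activity"), baseline diet score, "adherence and intervention grouping would contribute to significant HBI or FC concentration drop". It does not say whether the HBI drop in that model is the fall of 3 in item v, or whether the model is limited to active entrants.

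Two other statements bear on the point. For active entrants, Design and Methods says that after six weeks "the responders will continue with adding the dairy product". Objectives also plans to "examine the proportion of patients with significant feacal inflammation elevation following the dairy introduction".

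**The concern.** A rule that counts falls suits patients who start with symptoms. A patient who starts in remission has little or no room to fall, and success for that patient means not getting worse. Read literally, item v scores both kinds of patient with the same rule.

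Two things are at stake. First, if both strata enter the response analysis, active disease will appear to predict response partly because inactive patients cannot respond, and an unadjusted comparison of arms carries patients who can contribute no events. Second, remission, whether reached or kept, has no named HBI result. A difference between the diets in clinical relapse would have no pre-stated place in the report, and its definition could be chosen after the data are seen.

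**Working it through.** **Plan's own figure.** The SAP gives a total of 140 for power above 80% at two-sided 0.05, but no endpoint, effect size, SD or rates. It cannot be reproduced and says nothing about HBI. The documents also give no baseline HBI distribution and no expected share of remission entrants.

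**Step 1: who can meet the rule.** Inputs: a fall of at least 3 (item v); remission entry below 5 and active entry 5–14 (Design and Methods). Assumption: the HBI is an integer score with minimum 0. The final score must be at most baseline − 3.

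| Baseline HBI | Final score needed | Possible? |
|---|---|---|
| 0 | ≤ −3 | no |
| 1 | ≤ −2 | no |
| 2 | ≤ −1 | no |
| 3 | ≤ 0 | only by reaching 0 |
| 4 | ≤ 1 | only by reaching 0 or 1 |
| 5–14 | ≤ 2 to ≤ 11 | yes, for every score |

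So 3 of the 5 remission scores cannot respond. A patient who enters at 2 and stays at 2 (change 0) and one who goes from 2 to 9 (change +7) are both non-responders.

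**Step 2: response is not remission, even in active entrants.** A fall from 14 to 11 meets the rule, yet 11 lies inside the 5–14 range that the protocol calls active. The rule therefore measures neither induction nor maintenance of remission.

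**Step 3: effect of pooling.** All rates here are assumed: 70 per arm; active response 35% v 65%; remission entrants 30%, 50% or 70% of each arm, none of whom respond. Pooled response rates are the active rates times the active share: 0.7 × (35, 65) = 24.5% v 45.5%; 0.5 × (35, 65) = 17.5% v 32.5%; 0.3 × (35, 65) = 10.5% v 19.5%. Power by simulation (40,000 replicates; adjusted means Cochran-Mantel-Haenszel by activity):

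| Remission/active per arm | Crude pooled | Adjusted for activity | Active only |
|---|---|---|---|
| 21/49 | 78.0% | 86.4% | 86.4–86.6% |
| 35/35 | 54.7% | 69.1% | 69.1–70.5% |
| 49/21 | 26.8% | 48.1% | 48.5–49.0% |

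The crude comparison loses power; the adjusted one matches active-only. In the same setting active patients respond at (35 + 65)/2 = 50% on average and remission patients at 0%, so the activity association is produced by the definition.

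If some remission entrants (those at 3 or 4) do respond, the direction is not fixed. With equal remission response in both arms (5% or 10%), the adjusted test is 4–19 points below active-only (worst case 30.1% v 48.8%). With 3% v 9% or 5% v 15%, it is 1–25 points above (best case 74.0% v 49.0%).

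**Step 4: precision of a maintenance outcome.** Assume 90% v 70% of remission entrants still have HBI below 5. The 95% CI half-width is 1.96 × √(0.9×0.1/n + 0.7×0.3/n) = 1.96 × √(0.30/n).

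| n per arm | Half-width | Power, chi-squared / Fisher |
|---|---|---|
| 21 | 23.4 points | 37.8% / 25.9% |
| 35 | 18.1 points | 56.5% / 45.5% |
| 49 | 15.3 points | 72.5% / 62.7% |

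**The case against.** The strongest reply is that response was never meant for remission entrants. Design and Methods speaks of responders only among active entrants, and on that reading the floor problem and the built-in activity association both disappear. This reading is possible. But that sentence governs a step to the dairy stage; it is not tied to the fall of 3 and sets no analysis population. The week 4 and week 8 visits in item v and the unrestricted SAP model point the other way.

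Second, a reader might infer that pooling would spoil the treatment comparison. The documents do not support that. The SAP lists activity among the predictors, and step 3 shows that adjustment largely protects the comparison when remission entrants cannot respond. No passage commits to a crude pooled HBI response test, although the general line on categorical variables would permit one.

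Third, a reader might infer that clinical relapse cannot be measured. It can: HBI is collected at the scheduled visits, the cut-off of 5 is the protocol's own, and HBI could also be compared as a continuous variable. What is missing is a named outcome. The nearest named one, a significant rise in faecal inflammation after dairy, is biochemical and has no cut-off, and the dairy stage is described only for the exclusion-diet arm.

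Fourth, the power figures rest on assumed rates and have no consistent direction. That stands, and they are not offered as a reason for the change.

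**Conclusion.** The point holds in a limited form. As written, one response rule covers two strata, and 3 of the 5 remission scores cannot satisfy it. That count needs only an HBI minimum of 0; how many patients have those scores is unknown. If the strata are pooled, part of the activity association is an artefact of the definition and a crude comparison is diluted. No named HBI outcome measures remission induced or maintained, though both are aims.

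It would go too far to say that the plan definitely pools the strata, that the treatment effect would be biased, or that restricting the analysis gains power. The first is not stated, the second does not follow from the text, and on the third the calculations go either way. The issue affects a secondary outcome and an exploratory model, not the primary calprotectin goal. It should be fixed because a stated rule, followed literally, gives an artefactual result in one enrolled stratum, and the correction is a matter of wording.

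**What to change.** 1. State that the fall of at least 3 applies only to entrants with HBI 5–14. If the SAP's HBI-drop model means that rule, run it in those patients and omit the active/inactive predictor.
2. For entrants with HBI below 5, add the proportion still below 5 at week 4 and at week 8, by arm, with the difference and 95% CI.
3. For entrants with HBI 5–14, add the proportion below 5 at week 6, and the proportion below 5 at both week 6 and week 10. Keep all randomised active patients in the denominator, so that the arms are not compared only among patients selected by their response after randomisation. A response still present at week 10 would not serve as the remission measure, for the reason in step 2.
4. Report the two strata separately.

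The cost is outcome and SAP wording; item v already schedules HBI at these visits, and no treatment step changes. The downside is that each analysis uses one stratum and will be imprecise, so the new proportions should be read as estimates. Maintenance here means up to week 8 or 10, because item v lists no HBI at week 24.

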Current evidence-based nutritional guidelines for CD, arise mainly from epidemiological data and generally suggest a "healthy diet", characterized by an increased consumption of nutrient-dense foods along with a restricted intake of saturated and trans-fats, emulsifiers, thickeners, processed foods, unpasteurized dairy. According to the Dietary Guidance from the International Organization for the Study of Inflammatory Bowel Diseases (IOIBD), consensus was not reached for pasteurized dairy consumption among patients with CD. Based to evidence from epidemiology and animal models, the authors clarify that it is prudent for Crohn's disease patients to avoid lactose, given that lactase deficiency and lactose intolerance is common among patients with IBD. It was also noted that it could be prudent to reduce dairy fat and processed dairy rich in maltodextrins and emulsifiers (7). To date, no clear and strong recommendation can be given to follow a specific diet for inducing remission in patients with active CD, whereas the importance of a personalized nutritional approach is highlighted (8). Exclusive Enteral Nutrition (EEN) is the only well-established dietary therapy in CD and is commonly used for the induction of remission in mild to moderate pediatric CD (8-9, 12-13). Evidence according to EEN efficacy in adults is not consistent, which could more likely be explained by the compliance difficulty rather that by mechanistic differences (10-12). It is of interest, that fecal inflammation increases rapidly after food re-introduction following EEN in children (14). In this context, partial enteral nutrition (PEN) has sparked scientific interest as a possible maintenance dietary strategy. PEN has been shown to be beneficial in maintaining remission, but poor compliance due to low formula palatability and patients' fatigue remains an important barrier in the clinical practice. Moreover, PEN is inferior to EEN in inducing remission (13,15). Sigall Boneh and her colleagues evaluated a novel dietary intervention that combined PEN with an elimination diet (19). The Crohn's disease exclusion diet (CDED) is a whole-food, high protein, low saturated fat, low taurine, low heme, low food additives diet with exposure to fiber mainly from fruits, vegetables and complex carbohydrates. More specifically, CDED eliminates specific dietary components hypothesized to induce dysbiosis and appears to be effective in inducing and maintaining remission both in pediatric and adult population (16-19).

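### The entry criteria restrict recent drug changes but not recent or current nutritional therapy, so some patients can start with faecal calprotectin already changed by the kind of treatment under test

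*Combined protocol and SAP*

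**What the plan says.** The exclusion list in Eligibility Criteria contains one stability condition on treatment before entry: "Introduction of or change in dose of drug therapy within the past 8 weeks". The only diet-related exclusion is "Food allergies or intolerances, which do not permit participation in the study". Of the two inclusion criteria, one is "Participants must have an established diagnosis of CD" and the other is consent. Design and Methods admits patients with HBI 5–14, "or inactive disease (HBI<5) are eligible for enrolment", and sets no FC threshold at entry.

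The Objectives section states that "our primary goal is to investigate whether CDED with PEN could lead to a significant decrease in feacal calprotectin concentration". On allocation, Design and Methods says: "Patients will be randomly assigned 1:1 to either CDED plus PEN plus dairy products or PEN plus usual nutritional care". PEN is thus common to both arms, and CDED with the later dairy step belongs to one. For paired measures such as FC, the SAP says "we will calculate the percentage change for each patient relative to baseline", and it plans paired tests.

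The Background reports that PEN helps to maintain remission, that CDED appears effective in children and adults, and that "fecal inflammation increases rapidly after food re-introduction following EEN in children".

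**The concern.** The plan guards against recent drug changes at entry but applies no similar rule to the class of treatment it tests, although its own Background says that such treatment affects remission and faecal inflammation. Three kinds of patient could enter:

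- **Already on CDED.** Baseline FC may already be lowered. In the CDED arm this patient continues the diet; in the control arm the patient stops it. Neither is a start of CDED.
- **Already on PEN.** Baseline FC may already be lowered. PEN is then given in either arm, so there is less room for a fall in both.
- **Recently finished EEN.** The earlier effect may be wearing off during the study. In the CDED arm, an FC rise could be misread as dairy intolerance, because a stated aim is the proportion of patients whose FC rises after dairy is introduced.

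What is at stake is the before-after change in FC, which is how the primary goal is worded and how the SAP plans to express it.

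**Working it through.** **1. Is the restriction supplied elsewhere?** The exclusion list covers age, extensive resection, pregnancy or lactation, stoma or abscess, stricture, drug introduction or dose change, comorbidities, food allergy or intolerance, and current infection. Design and Methods adds only disease location and HBI. A food frequency questionnaire and 24-hour recalls are collected at baseline but are not tied to eligibility. The SAP's logistic model includes a baseline Mediterranean-diet score and adherence, but no term for earlier EEN, PEN or CDED. The gap is not closed at entry or in the analysis.

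**2. Inputs for an illustration.** The documents give no prevalence and no FC effect, so these are assumptions:
- f = fraction of entrants already on CDED, equal in both arms on average because of randomisation; range 5% to 20%.
- Starting CDED multiplies FC by 0.5; continuing it, by 1.
- Stopping CDED multiplies FC by 2; a control patient not previously on CDED, by 1.

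**3. Geometric-mean change.** CDED arm = 0.5^(1−f). Control arm = 2^f. Ratio = 0.5^(1−f) / 2^f = 0.5 for every f.

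| f | CDED arm | Fall in CDED arm | Control arm | Ratio |
|---|---|---|---|---|
| 0 | 0.500 | 50% | 1.000 | 0.5 |
| 5% | 0.518 | 48% | 1.035 | 0.5 |
| 10% | 0.536 | 46% | 1.072 | 0.5 |
| 20% | 0.574 | 43% | 1.149 | 0.5 |

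The within-arm fall shrinks; the between-arm ratio does not move.

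**4. Mean of individual percentage changes, same assumptions.** CDED arm = −50(1−f): −47.5%, −45% and −40% at f = 5%, 10% and 20%. Control arm = +100f: +5%, +10% and +20%. The difference is −52.5, −55 and −60 points, against −50 at f = 0. It widens only because a doubling counts as +100% and a halving as −50%. A rank test treats percentage change and ratio alike, so this concerns means only.

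**5. A different assumption gives the opposite direction.** The SAP's total of 140 cannot be reproduced, because no effect size, SD or rate is stated. Back-solved at 70 per arm, two-sided 0.05 and 80% power, it corresponds to a standardised difference of (1.960 + 0.842) × √(2/70) = 0.474. If prior users contributed no between-arm difference, the effect would be 0.474(1−f), and power would fall to 76%, 71% and 61% at f = 5%, 10% and 20%.

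The within-arm fall is reduced in steps 3 and 4. The between-arm contrast is unchanged, widened or diluted according to the assumption and the scale.

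**The case against.** Exposure may be uncommon. The Background describes EEN as mainly a paediatric treatment with compliance difficulty in adults, says PEN compliance is poor, and presents CDED with PEN as novel. The rates of 5% to 20% and the halving and doubling of FC are assumptions. This stands: the size is unknown.

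Randomisation should balance prior dietary therapy between arms. This also stands, and it rules out a confident statement about between-arm bias. It does not protect the paired before-after tests, and it does not turn a comparison of continuing with stopping into a test of starting.

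A reader might infer that the gap favours CDED, because control patients taken off the diet rebound: the control-arm factors of 1.035, 1.072 and 1.149 look like bias in that direction. The documents do not support this. Those factors count one arm only; the same kind of patient in the CDED arm has less room to fall, and under the symmetric assumption the two effects cancel exactly.

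A reader might also infer that FC must rise in either arm after recent EEN or PEN. That is not supported either. Both arms receive PEN from the start, and the rebound evidence cited concerns children after EEN, whereas this trial enrols adults.

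On dairy, FC is also sampled at week 4 or 6, before dairy is added, which offers a later reference than baseline. The plan does not say which reference the dairy aim uses, so the possible misreading is reduced but not removed.

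**Conclusion.** The omission is real and confined to the entry criteria. As written, the plan can enrol patients whose baseline FC already reflects the tested diet or a related one, and that baseline is the reference for the paired change and the percentage change. The main consequence is a diluted or distorted within-arm FC change. Under the stated assumptions, the CDED-arm geometric-mean fall goes from 50% to 48%, 46% or 43% with 5%, 10% or 20% prior users. The direction of any between-arm bias is undetermined. Because prevalence is not given and may be low, this is a cheap improvement, not a flaw that undermines the trial.

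**What to change.** Extend the existing drug-therapy exclusion to cover current or recent use of EEN, PEN, CDED or another therapeutic exclusion diet. The investigators should confirm the window; aligning it with the existing drug window is one example, but the documents give no dietary basis for a particular length. Check it with a direct question at screening: a 24-hour recall cannot show past use, and nothing in the plan says that the food frequency questionnaire captures formula or CDED use.

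If the investigators prefer not to exclude these patients, the lighter alternative is to record prior and current dietary therapy at baseline and stratify or adjust for it.

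The cost is one added phrase, one screening question, and a few patients deferred or screened out. The document is dated 24/08/2022 and anticipates recruitment from September 2022, so by its own timetable the change could precede enrolment.
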